## **6.2 Methods**

### **6.2.1 *Quality of life questionnaire***

The quality of life questionnaire is the NFKSI-19 questionnaire (see [Appendix 1](#)). It will be provided to the subjects in paper form. The handling is described in [6.3.4](#).

### **6.2.2 Activity questionnaire**

The activity questionnaire is a questionnaire asking for the activity of the patients using boxes to provide time of activity and visual analogue scales (VAS) (see [Appendix 2 and 3](#)). It was designed by [PPD](#) (German Sport University Cologne) for this study. There is a longer version for Visit 1 (see [Appendix 2](#)) and a shorter version for the following visits (see [Appendix 3](#)). It will be provided to the subjects in paper form. The handling is described in [6.3.4](#).

### **6.2.3 Actigraph measurement**

The Actigraph is the most frequently used tool to objectively assess physical activity in clinical and non-clinical studies. In detail, the Actigraph GT9X Link device will record raw data on physical activity (acceleration), steps, intensity of physical activity and body position.

The device will be worn by all subjects up to five times (less in case of early treatment discontinuation) for one week (seven days) after the respective visits. After wearing the device for one week, patients will complete the questionnaires listed under [6.3.1](#) and [6.3.2](#). After completing Visit 10 or after cabozantinib treatment discontinuation, subjects and the respective treating physician will receive a detailed report on their physical activity behaviour together with exercise recommendations. The Actigraph will only be used in centres where activity measurement is part of clinical routine.

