### 4.1 Overview

This is an international, multicentre, non-interventional prospective study. Data will be collected via electronic case report form (eCRF) by the sites.

This study will be conducted in Germany and Austria, which have a cabozantinib tablets Marketing Authorisation (MA) for first line use. MA for the cabozantinib-nivolumab combination as first line treatment in advanced or metastatic RCC was in March 2021. Patients intended to be treated with this combination can be enrolled as soon as the MA is in place for use of these products in the European Union.

Investigators will follow their individual therapeutic concept for the treatment with cabozantinib or cabozantinib-nivolumab combination in accordance with the current SmPC.

No out-of-routine diagnostic or therapeutic intervention is allowed during this study. All data recorded in this study originate from routine diagnostic and therapeutic procedures.

The investigator needs to inform the subject that personal and medical data will be recorded for this study. The subject has to give written informed consent for data collection, data processing and for monitoring purposes.

Data will be collected at the described visits:

- Visit 1 (baseline): enrolment visit,
- Visit 2 (approximately 4 weeks after baseline),
- Visit 3 (approximately 8 weeks after baseline),
- Visit 4 (approximately 12 weeks after baseline),
- Visit 5 (approximately 16 weeks after baseline),
- Visit 6 (approximately 24 weeks after baseline),
- Visit 7 (approximately 32 weeks after baseline),
- Visit 8 (approximately 40 weeks after baseline),
- Visit 9 (approximately 48 weeks after baseline),
- Visit 10 (approximately 56 weeks after baseline),
- Follow-up 1 (30 days after treatment discontinuation),
- Follow-up 2 (1 year after treatment discontinuation or 24 months after baseline if subjects reached visit 10).

The timing of the visits according to routine clinical practice is assumed to be close to the proposed schedule. If the timing does not meet the schedule, entries should be made at the visit nearest in time to the proposed schedule.

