If a subject discontinues the intake of cabozantinib or of cabozantinib-nivolumab combination at any visit before Visit 10, the follow-up period starts, and the next visit will be Follow-up 1. Discontinuation of the cabozantinib-nivolumab combination is defined as the permanent discontinuation of both study medications. i.e. as soon as one of the treatments is still ongoing the combination is not considered as discontinued. The Follow-up period can only start once both treatments have been permanently discontinued.

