### **6.2.4 Handling of device and questionnaires**

The device (Actigraph) and the questionnaires will be sent to the subjects first after informed consent (Visit 1) and thereafter at the respective weeks of Visit 4, 6, 8 and 10 (see [Table 2](#)). The subjects will receive a package from the researcher (German Sport University Cologne) including the device with an instruction and a help desk number, as well as the two questionnaires and a return package. After one week the subject will fill out the questionnaire and send the device and the questionnaires in the provided return package back to the vendor. The researcher will follow up with the subject if package is not received. Data handling is described in [12.3](#).

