##### *9.4.4.3 Exploratory Endpoint Analysis*

The evolution of activity level and quality of life between baseline and each time point (W12, W24, W40 and W56) will be described overall and also according to occupational and smoking status at initiation of Cabozantinib /cabozantinib-nivolumab combination in centers where this is part of the clinical routine.

Concomitant medications to cope with treatment related adverse event will be presented by therapeutic group and preferred name.

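### The activity report is triggered by stopping cabozantinib, so a combination subject still on nivolumab can receive exercise advice while activity and quality of life are still being measured

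*Protocol*

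**What the plan says.** Section 6.2.3 (Actigraph measurement) sets the release of the feedback: "After completing Visit 10 or after cabozantinib treatment discontinuation, subjects and the respective treating physician will receive a detailed report". It describes the content as feedback "on their physical activity behaviour together with exercise recommendations". Only cabozantinib is named as the drug whose discontinuation counts.

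Section 4.1 (Overview) defines discontinuation of the combination differently: "as soon as one of the treatments is still ongoing the combination is not considered as discontinued". It adds: "The Follow-up period can only start once both treatments have been permanently discontinued".

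Section 6.2.4 sends the device and both questionnaires first after consent and "thereafter at the respective weeks of Visit 4, 6, 8 and 10". Table 2 and section 6.1 give the same schedule (weeks 12, 24, 40 and 56). The device itself is restricted to centres where activity measurement is routine.

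Section 9.4.4.3 uses these data: "The evolution of activity level and quality of life between baseline and each time point (W12, W24, W40 and W56) will be described overall". Section 7.1.3 lists activity throughout therapy and quality of life among the exploratory endpoints.

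**The concern.** For monotherapy the trigger is harmless. Once cabozantinib stops, the subject moves to follow-up, where Table 2 schedules no activity or quality-of-life measurement.

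For the combination, the drug that triggers the report and the event that ends the visit schedule are no longer the same. A subject who drops cabozantinib and stays on nivolumab satisfies the report trigger but remains under observation. Exercise advice is aimed at the very quantity that is then measured again. In such a subject, later values cannot separate what followed from stopping cabozantinib from any response to the advice. Exposure to the advice also depends on the course of treatment, because a subject who stops only nivolumab does not meet the trigger.

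What is at stake is the interpretation of the W12 to W56 course of activity and quality of life in the combination cohort.

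**Working it through.** No planned figure is in dispute, so the check is mainly a comparison of sections.

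**Step 1: follow each type of subject before Visit 10.**

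| Subject stops | Report trigger met (6.2.3)? | Discontinued (4.1)? | Activity/QoL measurements continue? |
|---|---|---|---|
| Monotherapy: cabozantinib | Yes | Yes | No |
| Combination: both drugs | Yes | Yes | No |
| Combination: nivolumab only | No | No | Yes |
| Combination: cabozantinib only | **Yes** | **No** | **Yes** |

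Only the last row has the trigger met while measurement goes on.

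**Step 2: look for text that resolves it.** None was found. No section holds the report back until both drugs are stopped, and none ends activity or quality-of-life collection when cabozantinib alone stops. Section 6.2.3 says the device is worn fewer times after early treatment discontinuation, but does not say which drug is meant. If it meant cabozantinib alone, it would conflict with section 4.1, Table 2 and section 6.2.4. It would also govern only the device, so the questionnaires would still continue. The form for Amendment 1, as far as it is shown, records the both-drugs definition being added to section 4.1 and lists no change to the report trigger. That is consistent with wording carried over from the monotherapy design.

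**Step 3: how many later measurements could follow the report?** Count the scheduled weeks (12, 24, 40, 56) after an assumed week of stopping cabozantinib with nivolumab continuing:

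- Week 6: 4 (W12, W24, W40, W56)
- Week 18: 3 (W24, W40, W56)
- Week 30: 2 (W40, W56)
- Week 48: 1 (W56)

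**Step 4: how many subjects?** The protocol gives no rate for stopping cabozantinib first. The following is an assumption, shown as a range: affected subjects = 167 × assumed proportion, with 167 taken from section 9.3.

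- 2%: 167 × 0.02 = 3.3, about 3
- 5%: 167 × 0.05 = 8.4, about 8
- 10%: 167 × 0.10 = 16.7, about 17
- 15.3%: 167 × 0.153 = 25.6, about 26

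The 15.3% is the figure section 9.3 cites for discontinuation of either drug because of an adverse event. It is not split by drug, has no week-56 limit and leaves out other reasons for stopping. It is therefore neither an upper nor a lower bound here. The report is described as part of the actigraph programme, so the number in device-using centres would be smaller.

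**The case against.** The strongest reply is that section 6.2.3 says only that the report comes after one of two events and sets no deadline. A report held until the last measurement would also satisfy the sentence. This stands as far as it goes: early release is permitted, not required. But the text names cabozantinib discontinuation as a sufficient trigger, and anyone following it would be acting correctly in sending the report mid-series.

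Several stronger readings are tempting, and the documents do not support them.

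- *The study does alter activity, towards apparent recovery.* The protocol contains nothing on whether the report changes behaviour or quality of life, by how much, or in which direction. The supported statement is that it can.
- *The link between activity and adverse events is biased.* The secondary objective uses activity at baseline, which section 7.1.2 places within the first two weeks of treatment. Sections 7.2 and 9.4.6 also mention adverse events by activity level without a time point, but neither says that post-report activity is used.
- *The number affected can be had by allotting a share of the 15.3% to cabozantinib-only stops.* The documents give no such split.
- *The advice breaches the non-interventional rule.* Section 4.1 states: "No out-of-routine diagnostic or therapeutic intervention is allowed during this study". Whether exercise recommendations fall under it is a separate and arguable question. It would apply equally to monotherapy subjects and to those who complete Visit 10, all of whom remain in the study until Follow-up 2. Moving the report date would not settle it.

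It is also fair to say that handling of post-report values is analysis detail for the SAP. Its absence from the protocol is not held against the plan.

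**Conclusion.** The mismatch is real. Sections 6.2.3 and 4.1 use different discontinuation events, and for a combination subject who stops cabozantinib before nivolumab and before Visit 10 the exercise advice can arrive while activity and quality of life are still being measured. This can influence later values in the exploratory W12 to W56 description.

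The reach is narrow. It concerns one subset of one cohort, of a size the protocol does not allow one to derive: about 3 to 26 of 167 under assumed proportions of 2% to 15.3%, and fewer in device-using centres alone. Each such subject would have between one and four later measurements. No direction of bias is established. The primary endpoints, PFS, ORR, DCR and the objective on baseline activity and adverse events are untouched. The inconsistency itself depends on none of the assumed numbers. Severity: minor.

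**What to change.** Reconcile section 6.2.3 with section 4.1 by tying the report to the subject's last scheduled activity and quality-of-life measurement. It would go out either once the Visit 10 device and questionnaires have been returned, or once study treatment has been discontinued as section 4.1 defines it (both drugs for the combination). Naming the return of the Visit 10 package matters because the device is worn in the week after the visit.

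For any report already sent while measurement was continuing, record its date and describe the W12 to W56 values with and without post-report measurements.

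The cost is one sentence in the protocol, an instruction to the vendor handling the devices and, where needed, one recorded date. A few subjects and their physicians would receive the report later.

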### **6.2.4 Handling of device and questionnaires**

The device (Actigraph) and the questionnaires will be sent to the subjects first after informed consent (Visit 1) and thereafter at the respective weeks of Visit 4, 6, 8 and 10 (see [Table 2](#)). The subjects will receive a package from the researcher (German Sport University Cologne) including the device with an instruction and a help desk number, as well as the two questionnaires and a return package. After one week the subject will fill out the questionnaire and send the device and the questionnaires in the provided return package back to the vendor. The researcher will follow up with the subject if package is not received. Data handling is described in [12.3](#).

## **7 STUDY EVALUATIONS**

### **7.1 Endpoints & Evaluations**

In the framework of this non-interventional study, the nature and timing of subject assessments will be in accordance with routine medical practice.

#### **7.1.1 Primary Endpoints & Evaluations**

The primary endpoints are to describe the use of cabozantinib /cabozantinib-nivolumab combination in terms of:

- number and proportion of subjects with dose reduction of cabozantinib due to SAEs/AEs,
- number and proportion of subjects with dose interruption of cabozantinib and/or nivolumab due to SAEs/AEs,
- number and proportion of subjects with termination of cabozantinib /cabozantinib-nivolumab combination due to SAEs/AEs,
- injection delayed of nivolumab due to SAE/AE,

in subjects with advanced or metastatic renal cell carcinoma (mRCC) treated in real-life clinical setting in 1st line treatment overall and split by risk score

### 7.1.2 *Secondary Endpoints & Evaluations*

- To describe the effectiveness of cabozantinib /cabozantinib-nivolumab combination in advanced or metastatic RCC in real-life in terms of progression free survival (PFS), and best overall response (ORR & DCR).
  - Progression free survival is defined as the time between the start date of cabozantinib /cabozantinib-nivolumab combination and the date of progression or death from any cause. Disease progression is defined as either radiological progression assessed by the investigator using RECIST 1.1 [7] or clinical progression.
  - The best overall response is the best response assessed by investigator recorded during the treatment period.
  - ORR is defined as the proportion of subjects achieving complete or partial response.
  - DCR is defined as the proportion of subjects achieving a complete response, partial response or stable disease.
- To describe the impact of the activity level at the beginning of the treatment (within the first 2 weeks of cabozantinib /cabozantinib-nivolumab combination intake) on the occurrence of adverse events (AEs) using the actigraph and questionnaires
- To describe the use of cabozantinib /cabozantinib-nivolumab combination in subjects with advanced or metastatic renal cell carcinoma (mRCC) treated in real-life clinical setting in 1st line treatment split by histological subtype (clear cell and non-clear cell) in terms of:
  - Number and proportion of subjects with dose reductions of cabozantinib due to SAEs/AEs
  - Number and proportion of subjects with dose interruption of cabozantinib and/or nivolumab due to SAEs/AEs
  - Number and proportion of subjects with termination of cabozantinib /cabozantinib-nivolumab combination due to SAEs/AEs
  - Number and proportion of subjects with injection delayed of nivolumab due to SAEs/AEs

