#### **3.2 Secondary Objectives**

- To describe the effectiveness of cabozantinib tablets as monotherapy and the effectiveness of cabozantinib-nivolumab combination in advanced or metastatic RCC in real-life in terms of progression free survival (PFS) and best overall response (Objective Response Rate [ORR] & Disease Control Rate [DCR])
- To describe the use of cabozantinib tablets as monotherapy and the use of cabozantinib-nivolumab combination in real-life clinical setting in 1st line treatment split by histological subtype
- To describe all non-serious and serious adverse events (AEs / SAEs) and fatal outcomes per drug cohort
- To describe the impact of the activity level at baseline on the occurrence of adverse events (AEs)

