### Visit 1, baseline (enrolment):

- Date of informed consent signature
- Visit date
- Eligibility (verification of in- and exclusion criteria)
- Demographics (gender, year of birth)
- Significant Medical or Surgical History
- Disease history (date of renal cell carcinoma diagnosis, RCC stage at diagnosis, RCC stage at baseline (TNM), cancer histology, risk score either by IMDC or MSKCC)
- Prior Nephrectomies (occurrence and date)
- ECOG Performance Status
- Smoking status and Occupational status
- Vital Signs (Height and body weight, blood pressure)
- Inflammatory blood markers (hsCRP or CRP, as available, no safety marker)
- Quality of life questionnaire (NFKSI-19) after Visit 1 (within 2 weeks)
- Activity questionnaire after Visit 1 (within 2 weeks)
- Actigraph measurement (1 week) after Visit 1 (within 2 weeks) [only in centres where activity measurement is part of clinical routine]

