## 7.2 *Safety Evaluations*

In this prospective non-interventional study, investigators will collect and report all serious and non-serious adverse events, deaths, and all instances of ‘special situations’ as described in Section 10, starting at the time from signature of ICF up to Follow-up 1. The description of this safety evaluation is a secondary endpoint of this study. The adverse events will be described overall and also according to level of physical activity assessed by questionnaire and actigraph.

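### Activity called baseline is measured in the first two weeks on treatment, inside the AE window, so early AEs can create or inflate a link between low activity and more AEs

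*Protocol*

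**What the plan says.** Protocol 3.2 (and the synopsis) words the objective as "To describe the impact of the activity level at baseline on the occurrence of adverse events (AEs"). Section 7.1.2 gives the matching endpoint a different time frame: "To describe the impact of the activity level at the beginning of the treatment (within the first 2 weeks of cabozantinib /cabozantinib-nivolumab combination intake"), assessed by actigraph and questionnaires.

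The schedule agrees with 7.1.2. Under 6.1, Visit 1 lists "Actigraph measurement (1 week) after Visit 1 (within 2 weeks") and "Activity questionnaire after Visit 1 (within 2 weeks"). Under 6.2.4 the device and questionnaires "will be sent to the subjects first after informed consent (Visit 1"), and 6.2.3 has the questionnaires completed once the week of wear is over.

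Under 7.2, AEs are collected "starting at the time from signature of ICF up to Follow-up 1" and are to be described by level of physical activity. Section 9.4.6 repeats that description. Neither section ties the AE start date to the activity week.

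Section 9.4.4.3 uses the same first value as a reference: "The evolution of activity level and quality of life between baseline and each time point (W12, W24, W40 and W56").

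**The concern.** The exposure is named as a pre-treatment characteristic but measured on treatment, and its measurement window lies inside the period in which the outcome is collected. Section 2.1 lists fatigue, diarrhoea and nausea among the main low-grade AEs, each in more than 25% of cabozantinib subjects. Events of this kind can plausibly reduce a week of recorded movement. A subject with fatigue in week 1 may be classed as less active because of the fatigue, and the same fatigue then counts as an AE in the low-activity group. The arrow runs from AE to activity, while the word impact in 3.2 and 7.1.2 invites the reader to see it running the other way.

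At stake is one named secondary objective. The reference value for change in activity and quality of life has the same weakness: the first FKSI-19 covers the past 7 days and already asks about side effects of treatment (Appendix 1).

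**Working it through.** **Windows side by side**

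| Item | Window | Protocol section |
|---|---|---|
| Activity in the objective | Baseline | 3.2 |
| Activity in the endpoint | First 2 weeks of intake | 7.1.2 |
| Activity as scheduled | One week of wear, then questionnaires, within 2 weeks after Visit 1 | 6.1, 6.2.3, 6.2.4 |
| AE collection | Consent to Follow-up 1 | 7.2 |
| AE table by activity | No start day given | 7.2, 9.4.6 |

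No section requires a pre-dose measurement. The TEAE definition in 9.4.6 would remove events before the first dose, but not those in the first two weeks on treatment. The overlap therefore follows from the protocol's own definitions.

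**Size under a null model**

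The protocol gives no figure to reproduce here, and every input below is an assumption.

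- True activity A is standard normal and has no effect on AEs.
- A proportion pe has an AE in the first two weeks. This lowers measured activity by d SD.
- A proportion pl has a later AE, independent of everything else.
- Subjects are split at the median t of measured activity, where (1 − pe)Φ(t) + pe·Φ(t + d) = 0.5.

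Then:

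- early-AE rate, low half = pe·Φ(t + d)/0.5
- early-AE rate, high half = pe·[1 − Φ(t + d)]/0.5
- any-AE gap = (early-AE gap) × (1 − pl)

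Example with pe = 0.20, d = 0.5, pl = 0.40: t = −0.098 and Φ(t + d) = Φ(0.402) = 0.656. The early-AE rates are 0.20 × 0.656/0.5 = 26.2% and 0.20 × 0.344/0.5 = 13.8%, a gap of about 12.5 points. The any-AE gap is 12.5 × 0.60 = 7.5 points. Simulation of 2,000,000 subjects gives 55.7% against 48.3% for this case, in agreement.

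| pe | d (SD) | Early-AE gap | Any-AE gap, pl = 40% | pl = 60% | pl = 90% |
|---|---|---|---|---|---|
| 0.10 | 0.3 | 4.3 | 2.6 | 1.7 | 0.4 |
| 0.20 | 0.5 | 12.5 | 7.5 | 5.0 | 1.2 |
| 0.30 | 1.0 | 31.5 | 18.9 | 12.6 | 3.1 |

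Gaps are in percentage points, low minus high activity. With d = 0 the gap is zero. For later AEs of 40% or 60%, the any-AE gap runs from about 2 to 19 points. The early-AE column shows why a row for a single early event can be hit harder than the any-AE row.

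**After restricting to later onset**

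Counting only AEs that start after the window gives a gap of 0 (within 0.1 point) in every simulated scenario. The model makes this so, because later AEs were drawn independently of early ones. It shows that the overlap is removed, not that all bias is.

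**Reference value for change**

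If early AEs depress the first value by δ, the observed change is the true change plus δ. A true decline looks smaller, and an improvement looks larger.

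**The case against.** The strongest reply is that the missing AE start day is a detail for the SAP. Section 9.4 leaves derivation rules to that document, and a counting window for one descriptive table could be set there. This stands in part: a SAP could add the restriction. But the protocol itself fixes the on-treatment exposure window and the contradictory baseline label, and following it as written mixes the two directions of effect.

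Other limits also stand:

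- **All AEs since consent.** A reader might infer that the table counts everything from consent. Section 7.2 gives a collection period, not the analysis set for this table, and a TEAE-based table is possible. The overlap in the first two weeks on treatment remains either way.
- **Larger contrasts.** Assuming 40% early AEs and a drop of 0.5 SD, the outer activity tertiles show 53% against 27%. That counts early AEs only, in extreme groups, at a rate the protocol does not give. Under the same independence model the any-AE gap would be 26 × 0.7 = 18, 26 × 0.4 = 10 or 26 × 0.1 = 2.6 points for later-AE rates of 30%, 60% and 90%. The protocol's figure of 59.8% of METEOR subjects with dose reduction due to an AE (9.3) suggests that a low later-AE rate is unlikely.
- **A clean landmark.** If later AEs occurred in 45% after an early AE and 20% otherwise (assumed), the 53/27 split would still give 0.53 × 45 + 0.47 × 20 = 33% against 0.27 × 45 + 0.73 × 20 = 27% after the window.
- **Recall items as a substitute.** The Visit 1 questions on activity around diagnosis are answered after the wear week, and diagnosis may long precede advanced disease. They are a weak stand-in for pre-treatment activity.
- **Limited consequence.** The analysis is descriptive, any testing is exploratory, and actigraph data come only from centres where activity measurement is routine.

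**Conclusion.** The point holds as a design weakness in one secondary objective. Activity labelled baseline is an early on-treatment measure, and the AEs related to it are not limited to those starting afterwards. Early AEs that reduce activity can therefore create or inflate an association between low activity and more AEs.

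The direction depends on early AEs actually lowering measured activity. That is plausible but not shown in the protocol, which gives no onset times. The range of about 2 to 19 points rests on 10 to 30% early AEs, a drop of 0.3 to 1 SD, 40 or 60% later AEs, independence and a median split. It illustrates the mechanism and does not forecast this study.

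A reader might go further and conclude that any association seen will be an artefact, or that changes from the first value are always pulled toward zero. The protocol supports neither. A real association could coexist with the artefact, and a depressed reference understates declines but overstates improvements.

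**What to change.** 1. In 3.2 (with the matching synopsis text), 7.1.2 and 9.4.6, call the measure early on-treatment activity and replace impact with association.
2. In 9.4.6, and in line with it in 7.2, make the main table AEs with onset after the last day of the first actigraph and questionnaire week, among subjects still under AE observation on that day. Conditioning on AE observation rather than on continued treatment avoids dropping those who stopped early but are still followed for AEs.
3. Tabulate AEs that start before or during that week separately, by the same activity groups.
4. State that confounding by frailty or disease burden, and persistence of early AEs, remain after this restriction.
5. In 9.4.4.3, note that the reference value for activity and quality of life is on-treatment, so declines from it may be understated and improvements overstated.

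The cost is wording and one extra table, with no new data. The main table loses the events that start before or during the activity week and so has somewhat fewer events.
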